11.4.6.1. Major Hemorrhage

Major hemorrhage is defined as:

- Any Treatment-emergent hemorrhagic adverse event of Grade 3 or higher.*
- Any Treatment-emergent serious adverse event of bleeding of any grade.
- Any Treatment-emergent central nervous system hemorrhage/hematoma of any grade.

* All hemorrhagic events requiring transfusion of red blood cells should be reported as Grade 3 or higher AE per CTCAE.

Events meeting the definition of major hemorrhage will be captured as an event of special interest according to Section 11.4.6 above.

11.4.6.2. Pneumonitis

Pneumonitis has been reported in association with use of anti-PD-L1/anti-PD-1 antibodies (Brahmer 2012). Initial work-up should include a high-resolution CT scan, ruling out infection, and pulse oximetry. Additional assessments are to include pulmonary function tests and blood gases. Pulmonary consultation is recommended.

For Grade 2 pneumonitis that does not resolve to <Grade 1 within 3 days of maximal supportive care (including corticosteroids) or \geq Grade 3 pneumonitis, permanently discontinue MEDI4736.

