1.6.3 Ibrutinib and MEDI4736 Doses in Combination

Based on the above findings which describe the safety and PK profiles of ibrutinib and MEDI4736, the low discontinuation rate due to AEs, the low dose reduction rate, and the low

rate of high grade AEs, a dose of 560 mg ibrutinib PO daily continuously combined with a dose of 10 mg/kg MEDI4736 IV every 2 weeks for 12 months was chosen as the starting dose. (For MEDI4736 given every other week, the maximum number of doses is 24). As a lead-in to the first cycle, ibrutinib will be given for 7 days prior to starting MEDI4736 in order to obtain single agent PK and biomarker samples that can be compared to combination therapy. A dose deescalation design will be employed and in each cohort a sentinel subject will have a 3-day observation period prior to dosing of subsequent subjects to monitor for unexpected acute or overlapping toxicities.

2. STUDY OBJECTIVES

2.1 **Primary Objectives**

Phase 1b:

- To determine the recommended Phase 2 dose (RP2D) of ibrutinib in combination with MEDI4736 in subjects with relapsed or refractory lymphomas
- To determine the safety and tolerability of ibrutinib in combination with MEDI4736 in subjects with relapsed or refractory lymphomas

Phase 2:

• To evaluate the efficacy of ibrutinib in combination with MEDI4736 in subjects with relapsed or refractory lymphomas by assessing the ORR

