- If 3 or more DLTs are observed in the initial 6 subjects, enrollment into Cohort 1 will be stopped and the dose will be de-escalated to Cohorts -1A and -1B.

A similar 6+3 cohort design will be utilized in the dose de-escalation cohorts. If necessary, the dose de-escalation cohort -2 will be enrolled thereafter.

If a subject experiences a DLT during the DLT observation period, the subject will discontinue treatment. However, any subject(s) tolerating the dose level through the DLT observation period will continue with the same dose level of study drug even if subsequently-enrolled study subjects receive treatment at a dose de-escalation.

A Dose Level Review Committee (DLRC) will evaluate the safety data from each cohort of Phase 1b. Members of this committee will include participating investigators or designees as well as the Sponsor (invitees include: the Medical Monitor or designee, the clinical lead, a Drug Safety representative and a Biostatistician) (see Section 12.11).

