5.5 Study Treatment

All eligible subjects will be treated with ibrutinib PO and MEDI4736 IV in 28-day cycles. Prior to the first cycle, ibrutinib will be given daily for 7 days in the ibrutinib lead-in period prior to starting MEDI4736. On infusion days where pharmacokinetic, pharmacodynamic, or biomarker samples are drawn post-dose, MEDI4736 IV should be given first, with administration of ibrutinib as soon as possible after the end of infusion.

Missed doses of ibrutinib and MEDI4736 will not be made up. Dose modification of MEDI4736 will not be permitted.

Dosing of ibrutinib will continue up to 3 years as long as the subject is deriving clinical benefit (CR, PR, or SD) and the subject is not experiencing unacceptable toxicity. Dosing of MEDI4736 will continue for a total of 12 cycles of therapy if clinical benefit is seen without safety concerns. Toxicity may result in discontinuation or hold of one study drug while the other may continue to be dosed. Depending on the suspected relatedness to either agent (or both), the Investigator may perform dose modification and/or dose delays as per Section 5.6.1.4 and/or Section 5.6.2.5 at his or her clinical discretion. Re-treatment with MEDI4736 will not be allowed following completion of 12 cycles of treatment, regardless of any dose delays, missed doses, or following permanent discontinuation for any reason.

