	Grade 1 No dose modification required. However, consid holding study drug/study regimen dosing as clinical appropriate and during diagnostic work-up for oth etiologies	 For Grade 1 (Radiographic Changes Only): Monitor and closely follow up in 2-4 days for clinical symptoms, pulse oximetry (resting and exertion) and laboratory work-up and then as clinically indicated Consider pulmonary and infectious disease consult 	
	Grade 2 Hold study drug/study regimen dose until Grade ± resolution to Grade ≤1 • If toxicity worsens then	 For Grade 2 (Mild to Moderate New Symptoms): Monitor symptoms daily and consider hospitalization Discuss with study physician and consider 	
	 treat as Grade 3 or Grade 4 If toxicity improves to baseline then treat at nex scheduled treatment date 	 systemic steroids (eg, prednisone 1-2mg/kg/day or IV equivalent) Reimaging as clinically indicated If no improvement within 3-5 days, additional workup and treatment with IV methylprednisolone 2-4mg/kg/day should be 	
		 If no improvement within 3-5 days, further immunosuppressive therapy (eg, infliximab) should be considered. Once improving, gradually taper steroids over ≥4 weeks and consider prophylactic antibiotics Consider pulmonary and infectious disease consult 	
	Grade 3 or Permanently discontinue 4 study drug/study regimen	 For Grade 3 or 4 (severe or new symptoms, new/worsening hypoxia, life threatening): Discuss with study physician Pulmonary and infectious disease consult Hospitalize the subject Supportive Care (oxygen, etc.) Initiate empiric IV corticosteroids (eg, methylprednisolone or equivalent) at 1 to 4 mg/kg/day If no improvement within 3-5 days, additional workup and treatment with additional immunosuppressive therapy (eg, infliximab) should be considered Once improving, gradually taper steroids over ≥4 weeks and consider prophylactic antibiotics 	
Diarrhea/ Enterocolitis	Any Grade	 Monitor for symptoms that may be related to diarrhea/enterocolitis (abdominal pain, cramping, or changes in bowel habits) 	

Immuna Madiatad Daratiana			
		Immune-Mediated	I Keactions
	I	Dose Modifications	Toxicity Management
			 Subjects should be thoroughly evaluated to rule out any alternative etiology (eg, disease progression, infections, etc.) Steroids should be considered if an alternative etiology is not determined, even for low grade events, in order to prevent potential progression to higher grade event Use analgesics carefully; they can mask symptoms of perforation and peritonitis

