			_	Subjects should be evaluated to rule out any alternative etiology (eg, disease progression, infections, metabolic syndromes and medications, etc.). It should be noted that the diagnosis of immune-mediated peripheral neuromotor syndromes can be particularly challenging in subjects with underlying cancer, due to the multiple potential confounding effects of cancer (and its treatments) throughout the neuraxis. Given the importance of prompt and accurate diagnosis, it is essential to have a low threshold to obtain a neurological consult Neurophysiologic diagnostic testing (eg, electromyogram and nerve conduction investigations, and "repetitive stimulation" if myasthenia is suspected) are routinely indicated upon suspicion of such conditions and may be best facilitated by means of a neurology consultation Important to consider that the use of steroids as the primary treatment of Guillain-Barre is not typically considered effective. Subjects
				requiring treatment should be considered for plasmapharesis (or IVIgG, as an alternative)
	Grade 1	No dose modification	-	Discuss with the study physician Care should be taken to monitor subjects for sentinel symptoms of a potential decompensation as described above Consider a neurology consult unless the symptoms are very minor and stable
	Grade 2	Hold study drug/study regimen dose until resolution to Grade ≤ 1 Permanently discontinue study drug/study regimen if does not resolve to Grade ≤ 1 within 30 days or if there are	Gra - -	ade 2 : Moderate Discuss with the study physician Care should be taken to monitor subjects for sentinel symptoms of a potential decompensation as described above Obtain a Neurology Consult

Immune-Mediated Reactions		
	Dose Modifications	Toxicity Management
	signs of respiratory insufficiency or autonomic instability	 Sensory neuropathy/neuropathic pain may be managed by appropriate medications (eg, gabapentin, duloxetine, etc.) MYASTHENIA GRAVIS:
		 Steroids may be successfully used to treat Myasthenia Gravis. Important to consider that steroid therapy (especially with high doses) may result in transient worsening of myasthenia and should typically be administered in a monitored setting under supervision of a consulting neurologist.
		 Subjects unable to tolerate steroids may be candidates for treatment with plasmapharesis or IVIgG. Such decisions are best made in consultation with a neurologist, taking into account the unique needs of each subject.

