5.7 Criteria for Permanent Discontinuation of Study Drug

Investigators are encouraged to keep a subject who is experiencing clinical benefit in the study unless significant toxicity puts the subject at risk or routine noncompliance puts the study outcomes at risk. For a list of criteria for permanent discontinuation of study treatment, refer to Section 9.2.

Subjects who withdraw for any reason other than those specified in Sections 5.4 and 9.2 will not be replaced. An End-of-Treatment Visit for ibrutinib (Section 8.3.1) and an End-of-Treatment Visit for MEDI4736 (Section 8.3.2) are required for all subjects except for those subjects who have withdrawn full consent.

6. CONCOMITANT MEDICATIONS/PROCEDURES

Concomitant therapies must be recorded from the time of ICF signing until 30 days after the last dose of ibrutinib and 90 days after the last dose of MEDI4736.

6.1 **Permitted Concomitant Medications**

Supportive medications in accordance with standard practice (such as for emesis, diarrhea, etc.) are permitted. Use of neutrophil growth factors (filgrastim and pegfilgrastim) or red blood cell growth factors (erythropoietin) is permitted per institutional policy and in accordance with American Society of Clinical Oncology (ASCO) guidelines (Smith 2006). Transfusions may be given in accordance with institutional policy.

Short courses (\leq 14 days) of corticosteroid treatment for non-cancer related medical reasons considered unrelated to study treatment (eg, unrelated joint inflammation, asthma exacerbation, rash, antiemetic use) at doses that do not exceed 100 mg per day of prednisone or equivalent are permitted after discussion with the Medical Monitor. During corticosteroid treatment with >10 mg per day of prednisone or equivalent, MEDI4736 should be held until event resolution to Grade \leq 1 or baseline; thereafter, MEDI4736 administration may be resumed at the next scheduled dose. For MEDI4736-related adverse reactions, please follow the corticosteroid and dose administration guidelines in Section 5.6.2.5.

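### Slow-resolving Grade 2 pneumonitis: Section 11.4.6.2 stops MEDI4736 permanently, Table 4 allows it to resume, and the protocol does not say which rule governs

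*Protocol*

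**What the plan says.** Protocol Section 11.4.6.2, within the adverse events of special interest, sets a stopping condition: "For Grade 2 pneumonitis that does not resolve to <Grade 1 within 3 days of maximal supportive care (including corticosteroids"). The same sentence adds Grade 3 or higher as a second trigger, and the action for both is permanent: "Grade 3 pneumonitis, permanently discontinue MEDI4736".

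Table 4 in Section 5.6.2.5 treats Grade 2 pneumonitis differently. Drug is held until the event falls to Grade 1 or lower, and then: "If toxicity improves to baseline then treat at nex scheduled treatment date". If there is no improvement, the row steps up treatment at intervals of 3–5 days, first to IV methylprednisolone and then to further immunosuppression such as infliximab. The dose action stays a hold throughout. Permanent discontinuation appears only in the Grade 3 or 4 row, which a Grade 2 event reaches only by worsening.

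Other sections bear on which rule a site would apply:

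- Section 6.1, for reactions related to MEDI4736: "please follow the corticosteroid and dose administration guidelines in Section 5.6.2.5".
- Section 5.7 refers to Section 9.2 for permanent-stop criteria. Section 9.2 lists unacceptable toxicity in general terms and does not mention pneumonitis.
- Section 5.5 bars re-treatment with MEDI4736 after 12 cycles regardless of delays, "missed doses, or following permanent discontinuation for any reason".

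**The concern.** These are two current instructions for one drug and one clinical event, and they lead to opposite actions. Pneumonitis is an event of special interest, so this is a poor place for ambiguity.

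Either error has a cost. A site that works from Table 4 would re-expose a subject whom Section 11.4.6.2 says must stop. A site that works from Section 11.4.6.2 makes a decision that Section 5.5 does not allow to be reversed, for a subject whom Table 4 would have let resume. The SAP (Table 2) summarises treatment-emergent events leading to treatment discontinuation, so different practice between sites would also blur that summary.

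**Working it through.** The plan states no figure on this point, so the check is mainly a comparison of text.

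**1. The two rules side by side, for Grade 2 pneumonitis**

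| | Section 11.4.6.2 | Table 4, Grade 2 row |
|---|---|---|
| Trigger for a permanent stop | Unresolved after 3 days of maximal supportive care | None at Grade 2; only after worsening to Grade 3 or 4 |
| Time limit | 3 days | None |
| Late return to baseline | Stop stands | Resume at the next scheduled infusion |
| Scope | MEDI4736 | Study drug or regimen |

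**2. A worked case.** Suppose the event is still Grade 2 on day 4 of maximal care and back to baseline by day 10. Table 4 resumes MEDI4736 at the next scheduled date. Section 11.4.6.2 has already stopped it for good.

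**3. Can a time limit be read into the Table 4 row?** Table 4 writes such limits where it wants them. Its Grade 2 row for peripheral neuromotor syndromes reads "Permanently discontinue study drug/study regimen if does not resolve to Grade" 1 or lower within 30 days. The pneumonitis row has no counterpart, although it plans explicitly for slow cases.

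**4. Does another section settle it?** Inside the Phase 1b DLT window, yes. Section 5.3 makes Grade 2 or higher pneumonitis a DLT if it has not resolved to Grade 1 or lower within 3 days of starting maximal supportive care, provided it is at least possibly related. Section 5.2 then applies: "If a subject experiences a DLT during the DLT observation period, the subject will discontinue treatment". That agrees with Section 11.4.6.2. Outside that window nothing settles it, so the conflict is live for all of Phase 2 and after Cycle 1 in Phase 1b.

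**5. What turns on it per subject.** Two infusions per cycle for 12 cycles give 2 × 12 = 24, and Section 1.6.3 agrees: "the maximum number of doses is 24". A permanent stop after infusion k forfeits at most 24 − k:

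- k = 2 (Cycle 1 Day 15): 24 − 2 = 22. In Phase 1b this point lies inside the DLT window, so the figure applies to a Phase 2 subject.
- k = 4 (Cycle 2 Day 15): 24 − 4 = 20.
- k = 12 (Cycle 6 Day 15): 24 − 12 = 12.

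These are upper limits. They assume the subject would otherwise complete 12 cycles, and doses missed during the hold are not made up.

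**6. A symbol.** Section 11.4.6.2 prints resolution to below Grade 1, where Section 5.3 has Grade 1 or lower. This may be a slip or a fault in the text extraction. The conflict exists under either reading.

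**The case against.** The best reply is that the two rules differ in status. Section 5.6.2.5 introduces Table 4 as guidance to support the investigator's judgment, and Section 5.5 leaves modifications under it to clinical discretion. Section 11.4.6.2 is a direct, event-specific order. A site could obey both by holding while the event is Grade 2 and stopping once the 3-day condition is met, since Table 4 does not forbid that. Nor does Table 4 ever dose during an active Grade 2 event.

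There are also safeguards. The row calls for daily monitoring and discussion with the study physician, events of special interest go to the sponsor within 24 hours, and infusions are two weeks apart. The 3-day clock runs from maximal supportive care, which is not defined. If that means the later steps in Table 4, fewer cases fall in the overlap. Finally, the Section 6.1 pointer closes a paragraph about corticosteroids and is not a ranking of rules.

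Much of this stands as a limit on size. The overlap is small, and the safeguards lower the chance of an error. But the reading in which the stricter rule prevails is inferred, not written. Section 5.5 sends dose changes to Sections 5.6.1.4 and 5.6.2.5, and Section 6.1 sends MEDI4736-related reactions to 5.6.2.5, whereas the stop sits in the reporting chapter with no cross-reference from Table 4. A call to the study physician prompts a conversation without saying which rule applies.

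**Conclusion.** The concern holds. For Grade 2 pneumonitis unresolved after 3 days of maximal supportive care that later returns to baseline, the protocol both resumes MEDI4736 and stops it permanently, with no stated precedence. The agreement between Sections 5.3, 5.2 and 11.4.6.2 suggests that the Table 4 row is the outlier.

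The scope is narrow. The documents give no incidence, so the number of subjects affected cannot be estimated; only the upper limit of 24 − k infusions per affected subject can. The Grade 3 and 4 rules already agree, and sample size, type I error and the response-rate test are untouched. This is a correction the sponsor should make for subject safety and consistent conduct. It does not threaten the trial's conclusions.

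**What to change.** Add one sentence to the Grade 2 pneumonitis row of Table 4: MEDI4736 is stopped for good if the event has not come down to Grade 1 or lower within 3 days of starting maximal supportive care, corticosteroids included. Confirm or correct the symbol in Section 11.4.6.2 so that it also means Grade 1 or lower, as in Section 5.3. Because the row covers the whole regimen while the stop concerns MEDI4736 only, the amendment should also say that ibrutinib remains under the existing hold, if that is the intent.

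If the sponsor prefers hold-and-resume, delete the 3-day stop from Section 11.4.6.2 outside the DLT window instead.

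The cost is negligible: one table row and one symbol in the next amendment. The drawback of the first option is that a few subjects whose Grade 2 event resolves slowly lose the chance to resume MEDI4736.

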11.4.6.3. Hypersensitivity Reactions

Hypersensitivity reactions as well as infusion-related reactions have been reported with anti PD-L1 and anti-PD-1 antibodies (Brahmer 2012). As with the administration of any foreign protein and/or other biologic agents, reactions following the infusion of monoclonal antibodies can be caused by various mechanisms, including acute anaphylactic (IgE-mediated) and anaphylactoid

reactions against the monoclonal antibody, and serum sickness. Acute allergic reactions may occur, may be severe, and may result in death. Acute allergic reactions may include hypotension, dyspnoea, cyanosis, respiratory failure, urticaria, pruritis, angioedema, hypotonia, urticaria, arthralgia, bronchospasm, wheezing, cough, dizziness, fatigue, headache, hypertension, myalgia, vomiting and unresponsiveness.

11.4.6.4. Hepatic Function Abnormalities (Hepatotoxicity)

Increased transaminases have been reported during treatment with anti-PD-L1/anti-PD-1 antibodies (Brahmer 2012). Inflammatory hepatitis has been reported in 3% to 9% of patients treated with anti CTLA-4 monoclonal antibodies (eg, ipilimumab). The clinical manifestations of ipilimumab-treated patients included general weakness, fatigue, nausea and/or mild fever and increased liver function tests such as AST, ALT, alkaline phosphatase, and/or total bilirubin.

Cases where a subject shows AST or ALT $\ge 3 \times ULN$ or total bilirubin $\ge 2 \times ULN$ may need to be reported as SAEs. These cases should be reported as SAEs if after evaluation they meet the criteria for a Hy's Law case or if any of the individual liver test parameters fulfill any of the SAE criteria. For potential Hy's Law and Hy's Law to be met, the elevation in transaminases must precede or be coincident with (ie, on the same day) the elevation in total bilirubin, but there is no specified time frame within which the elevations in transaminases and total bilirubin must occur.

Criteria for Hy's Law (FDA Guidance 2009):

- The drug causes hepatocellular injury, generally shown by a higher incidence of 3-fold or greater elevations above the ULN of ALT or AST than the (non-hepatotoxic) control drug or placebo
- Among trial subjects showing such aminotransferase elevations, often with aminotransferases much greater than 3 x ULN, one or more also show elevation of serum total bilirubin to >2 x ULN, without initial findings of cholestasis (elevated serum alkaline phosphatase)
- No other reason can be found to explain the combination of increased aminotransferases and total bilirubin, such as viral hepatitis A, B, or C; pre-existing or acute liver disease; or another drug capable of causing the observed injury.

12. STUDY ADMINISTRATION AND INVESTIGATOR OBLIGATIONS

12.1 Regulatory and Ethical Compliance

This clinical study was designed and will be implemented in accordance with the protocol, the ICH Harmonized Tripartite Guidelines for Good Clinical Practices, with applicable local regulations (including US Code of Federal Regulations [CFR] Title 21 and European Directive 2001/20/EC), and with the ethical principles laid down in the Declaration of Helsinki.

12.2 Institutional Review Board (IRB), Research Ethics Board (REB) and Independent Ethics Committee (IEC) Approval

The Investigator will submit this protocol, the ICF, IB, and any other relevant supporting information (eg, all advertising materials or materials given to the subject during the study) to the appropriate IRB/REB/IEC for review and approval before study initiation. Amendments to the protocol and informed consent form must also be approved by the IRB/REB/IEC before the implementation of changes in this study.

The Investigator is responsible for providing the IRB/REB/IEC with any required information before or during the study, such as SAE expedited reports or study progress reports.

The IRB/REB/IEC must comply with current United States (US) regulations (§21 CFR 56) as well as country-specific national regulations and/or local laws.

The following documents must be provided to Pharmacyclics or its authorized representative before entering subjects in this study: (1) a copy of the IRB/REB/IEC letter that grants formal approval; and (2) a copy of the IRB/REB/IEC-approved ICF.

